2.4.1.2 Multiple assessments within visit windows

When there are multiple assessments in a particular visit window, the following rules are applied to select one value “representing” the subject in summary statistics in a visit window (See [Table 2-2](#)).

The definition of baseline assessment is included in [Section 2.1.1.3](#). For post-baseline visit windows the following applies (unless otherwise specified):

- for *quantitative variables*, the *closest* to the actual visit is chosen (if two assessments have the same distance, then the earlier one will be chosen),

- for *qualitative variables*, the *worst* record is selected. It is noted that in the analyses performed, *worst* case is always well defined (e.g., for urine protein values “+” and “++”, the worst case is defined as “++”),
- in case qualitative variables are based on quantitative variables, e.g. BASDAI50, the visit will be assigned to the quantitative variable, and this visit will be used for the derived qualitative variable.

Table 2-2 Rules for selecting values for analysis within a given visit window

| Timing of measurement | Type of data | Rule |
|------------------------|--------------|---|
| Baseline | All data | 
The last non-missing measurement made prior to or on the date of administration of the first dose of study treatment (the reference start date / Day 1). If a patient did not receive any dose of study treatment, then the randomization date will be used. Only date part is considered if just one assessment on Day 1.
 
If there are multiple assessments on Day 1, following rules will apply:
 
 If assessment time exists, 
 * select the last available measurement prior to reference start date/time considering time; * if no measurement prior to reference start date/time considering time, select the earliest measurement post reference start date/time considering time. If assessment time does not exist, select the available measurement from the lowest CRF visit number. 
For MRI, a baseline value is the last measurement prior to dosing if available. Otherwise, take the first value within 7 days post dosing.
 |
| Post-baseline efficacy | All data | 
For visits without switch of treatment in the window, the measurement closest to the target will be used. In the event two measurements are taken equally apart (e.g. 1 before target date and 1 after) the first one will be used.
 
For visits during which the patient switchers from placebo to AIN the following will be done based on whether the patient met the rescue criteria:
 
 if the analysis visit window is \leq week 16, then 
 - if available, the closest measurement to the target date which is ON or BEFORE the switch date will be used (i.e. the closest measurement to target which is on placebo) - if there are no data on or before the switch then the closest measurement to the target date after the switch will be used if the analysis visit window is $>$ week 16, then 
 - if available, the closest measurement to the target date which is AFTER the switch date will be used (i.e. the closest measurement to target which is on AIN) - if there are no data AFTER the switch then the closest measurement to the target date before the switch will be used 
Cases where the same parameter is recorded more than once on the same date will be handled as follows:
 
* if time of completion exists the earliest measurement will be used;
 |

| | | |
|----------------------|---|---|
| | | * if time does not exist the measurement from the lowest CRF visit number will be used |
| Post-baseline safety | Summary visit information (e.g. lab, ECG, etc.) | 
For visits without switch of treatment in the window, the measurement closest to the target will be used. In the event two measurements are taken equally apart (e.g. 1 before target date and 1 after) the first one will be used.
 
For visits during which the patient switches from placebo to AIN the following will be done based on whether the patient met the rescue criteria:
 
 a. if the analysis visit window is <= week 16, then 
 - if available, the closest measurement to the target date which is ON or BEFORE the switch date will be used (i.e. the closest measurement to target which is on placebo) - if there are no data on or before the switch then the closest measurement to the target date after the switch will be used b. if the analysis visit window is > week 16, then 
 - if available, the closest measurement to the target date which is AFTER the switch date will be used (i.e. the closest measurement to target which is on AIN) - if there are no data AFTER the switch then the closest measurement to the target date before the switch will be used 
Cases where the same parameter is recorded more than once on the same date will be handled as follows:
 
 * if time of completion exists and differs, the earliest measurement will be used; * if time of completion is the same, the measurements will be averaged; * if time does not exist the measurement from the lowest CRF visit number will be used. |
| Post-baseline safety | Notable abnormalities (e.g. lab) | The most extreme measurement in the window will be used. Note this means a patient can have a notably high and notably low measurement within a window. |

2.4.2 Prior, concomitant and post therapies

Prior and concomitant medications will be summarized in separate tables by treatment group. Concomitant treatments will be displayed by study period as appropriate.

Prior medications are defined as treatments taken and stopped prior to first dose of study treatment. Any medication given at least once between the day of first dose of randomized study treatment and within 84 days after the last dose will be a concomitant medication, including those which were started pre-BSL and continued into the period where study treatment is administered.

Medications will be presented in alphabetical order, by Anatomical Therapeutic Classification (ATC) codes and grouped by anatomical main group. Tables will show the overall number and percentage of participants receiving at least one treatment of a particular ATC code and at least one treatment in a particular anatomical main group.

Significant prior and concomitant non-drug therapies and procedures will be summarized by primary system organ class and MedDRA preferred term.

Prior surgeries and procedures are defined as surgeries and procedures done prior to first dose of study treatment. Any surgeries and procedures done between the day of first dose of study treatment and within 84 days after the last dose will be a concomitant surgeries and procedures, including those which were started pre-BSL and continued into the period where study treatment is administered.

The number and percentage of participants receiving prior and concomitant nr-axSpA therapy will be presented by randomized treatment group as well as the reasons for stopping their therapies (primary lack of efficacy, secondary lack of efficacy, lack of tolerability, other) and the total duration of exposure to nr-axSpA therapies previously. The use of NSAIDs, systemic corticosteroids and DMARD (MTX, Leflunomide, sulfasalazine) use will be summarized.

Prior or concomitant medication will be identified by comparing recorded or imputed start and end dates of medication taken to the reference start date.

2.5 Analysis of the primary objective

The primary objective of this study is to assess the efficacy of secukinumab relative to placebo at week 16 based on the proportion of participants achieving an ASAS40 response in TNF- α naïve participants. The consistency of the treatment difference between this bridging study and the global study will be evaluated.

2.5.1 Primary endpoint

The primary efficacy variable is response to treatment according to the ASAS40 criteria at Week 16 in TNF- α naïve participants with active nr-axSpA. The analysis of the primary variable will be based on the FAS participants.

The clinical question of interest is: What is the effect of secukinumab 150 mg s.c. versus placebo on ASAS40 response after 16 week-treatment in Chinese patients with active nr-axSpA who are TNF- α naïve?

The justification for targeting this treatment effect is that we wish to estimate the effect of the study drug for the full duration when administered without dose changes.

The primary estimand is described by the following attributes:

- A. Population: defined through appropriate inclusion/exclusion criteria to reflect the targeted nr-axSpA population
- B. Variable: composite of remaining in the study and on randomized treatment through 16 weeks and achieving ASAS40 response at Week 16
- C. Treatment of interest: Secukinumab 150 mg s.c. and Placebo
- D. Intercurrent event: the intercurrent event of discontinuation from treatment or study prior to Week 16 has been addressed via the variable definition
- E. Population-level summary: difference in proportions of responders between secukinumab 150 mg and placebo groups

2.5.2 Statistical hypothesis, model, and method of analysis

The primary analysis will be conducted via logistic regression with treatment and stratification factor (CRP+/MRI+, CRP+/MRI-, CRP-/MRI+) as factors and weight as a covariate. Difference in marginal response proportions between secukinumab regimen and placebo regimen and the corresponding 95% confidence interval (CI) will be computed utilizing the logistic regression model fitted.

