2.3.2 Demographics and baseline characteristics

The following common background and demographic variables will be summarized:

Continuous variables:

- Age
- Height
- Weight
- Body mass index (BMI) = (body weight in kilograms) / (height in meters)²

Categorical variables:

- Age categories (<45 years, 45 years and older)
- Gender
- Race
- Ethnicity
- Smoking status at baseline

Baseline disease characteristics will also be summarized for the following variables:

- Participant's global assessment of disease activity and other ASAS components, hsCRP (mg/L and > ULN), ESR (mm/h), prior use (yes/no) of TNF- α inhibitors, use (yes/no) and separate NSAIDs (yes/no) and dose of concomitant NSAIDs, MTX (yes/no) and MTX (mg/week), susulfasalazine (yes/no) and sulfasalazine (g/day) and systemic corticosteroids (yes/no) and systemic corticosteroids (mg/day) at randomization, time since first diagnosis of nr-axSpA and time since onset of inflammatory back pain(years), HLA-B27, [REDACTED], total back pain (VAS), nocturnal back pain (VAS), total BASDAI score, spinal pain (BASDAI question #2), total BASFI score, [REDACTED], [REDACTED] and each randomization strata level (CRP+/MRI+, CRP-/MRI-, CRP+/MRI-).

Unless otherwise specified, summary statistics will be presented for continuous variables for each treatment group and for all subjects (total) in the randomized set. The number and percentage of subjects in each category will be presented for categorical variables for each treatment group and all subjects (total) in the randomized set.

Unless otherwise specified, analyses will be based on the randomized set.

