2.6.2 Statistical hypothesis, model, and method of analysis

ASAS40 at Week 16

The proportion of patients meeting the response criteria will be evaluated using a logistic regression model with treatment group and stratification factor (CRP+/MRI+, CRP+/MRI-, CRP-/MRI+) as factors and weight as a covariate.

ASAS 5/6 at Week 16

The proportion of participants meeting the response criteria will be evaluated using a logistic regression model with treatment group and stratification factor (CRP+/MRI+, CRP+/MRI-, CRP-/MRI+) as factors and weight as a covariate.

BASDAI at Week 16

Between-treatment differences in the change from baseline in BASDAI will be evaluated using MMRM with treatment group, stratification factor (CRP+/MRI+, CRP+/MRI-, CRP-/MRI+) and analysis visit as factors and baseline BASDAI score and weight as continuous covariates. Treatment by analysis visit and baseline BASDAI score by analysis visit will be included as interaction terms in the model. An unstructured covariance structure will be assumed for the model.

BASDAI50 at Week 16

The proportion of participants meeting the response criteria at Week 16 will be evaluated using a logistic regression model with treatment group and stratification factor (CRP+/MRI+, CRP+/MRI-, CRP-/MRI+) as factors and baseline weight and baseline BASDAI score as covariates.

hsCRP at Week 16

For the change in hsCRP, since evidence from the literature would suggest that the data are not normally distributed (Huffman et al. 2006), analysis will be performed on the \log_e ratio of the treatment value vs baseline value (calculated by dividing the post-baseline value by the baseline value and then applying the \log_e transformation) to normalize the distribution of hsCRP at each analysis visit. Between-treatment differences in the change in hsCRP relative to baseline will be evaluated using MMRM with treatment group, stratification factor (CRP+/MRI+, CRP+/MRI-, CRP-/MRI+) and analysis visit as factors and \log_e baseline hsCRP and weight as continuous covariates. Treatment by analysis visit and \log_e baseline hsCRP by analysis visit will be included as interaction terms in the model. An unstructured covariance structure will be assumed for the model. The estimate and the 2-sided 95% confidence intervals obtained from the model will be back transformed to the original scale.

BASFI at Week 16

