Between-treatment differences in the change from baseline in BASFI will be evaluated using MMRM with treatment group, stratification factor (CRP+/MRI+, CRP+/MRI-, CRP-/MRI+) and analysis visit as factors and baseline BASFI score and weight as continuous covariates. Treatment by analysis visit and baseline BASFI score by analysis visit will be included as interaction terms in the model. An unstructured covariance structure will be assumed for the model.

SI joint edema on MRI at Week 16

The change from baseline to Week 16 in inflammation measured by SI joint total edema score will be evaluated using an ANCOVA model with treatment group, stratification factor (CRP+/MRI+, CRP+/MRI-, CRP-/MRI+) as factors, and weight and baseline inflammation score as covariates. Missing data will be imputed using multiple imputation prior to running ANCOVA.

ASAS20 at Week 16

The proportion of participants meeting the response criteria will be evaluated using a logistic regression model with treatment group and stratification factor (CRP+/MRI+, CRP+/MRI-, CRP-/MRI+) as factors and weight as a covariate.

SF-36 PCS at Week 16

Between-treatment differences in the change from BSL in SF36-PCS summary score will be evaluated using a MMRM with treatment group, stratification factor (CRP+/MRI+, CRP+/MRI-, CRP-/MRI+) and analysis visit as factors and baseline SF-36 PCS score and weight as covariates. Treatment by analysis visit and baseline SF-36 PCS score by analysis visit will be included as interaction terms in the model. An unstructured covariance structure will be assumed for the model.

ASQoL at Week 16

Summary statistics of observed data by visit and change from baseline in ASQoL will be provided for each treatment regimen. Between-treatment differences will be evaluated using MMRM. Treatment group, stratification factor (CRP+/MRI+, CRP+/MRI-, CRP-/MRI+) and analysis visit will be included as categorical factors and baseline ASQoL scores and weight as continuous covariates. Treatment by analysis visit and baseline ASQoL scores by analysis visit will be included as interaction terms in the model. An unstructured covariance structure will be assumed for the model.

ASAS partial remission at Week 16

Response at Week 16 to ASAS partial remission criteria will be evaluated using a logistic regression model with treatment and stratification factor (CRP+/MRI+, CRP+/MRI-, CRP-/MRI+) as factors and weight as a covariate.

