3.1 Primary endpoint(s)

As it is a bridging study for China registration, this study will pursue an estimation strategy rather than formal hypothesis testing of treatment difference.

Analysis of the phase III study CAIN457H2315 with secukinumab in nr-axSpA showed a placebo response rate of about 29.2% and a secukinumab 150 mg response rate of 41.5% after 16 weeks for ASAS40 in TNF- α naïve participants. Assuming 10% of randomized participants will be TNF- α IR and 90% of randomized participants will be TNF- α naïve. With 134 participants, 120 of them are TNF- α naïve (1:1 ratio to two groups), then there are approximately 77.3% probability to show at least 50% global treatment difference (6.15%) and approximately 90.7% probability to show positive treatment difference.

Table 3-1 Probability of Success with Different Observed Response Rates of ASAS40 in TNF- α naïve participants

| | Observed Response Rate | | | 95% CI of (p ₁ -p ₂) | Aimed Treatment Difference | Criterion 1 | | Criterion 2 | |
|------------|-------------------------------|---------------------------|--------------------------------|---|----------------------------|-------------|----------------------------|-------------|--|
| | Secukinumab (p ₁) | Placebo (p ₂) | p ₁ -p ₂ | | | PoS | Aimed Treatment Difference | PoS | |
| Scenario 1 | 0.395 | 0.292 | 0.103 | (-0.066, 0.272) | > 0.0615 | 0.699 | > 0 | 0.864 | |
| Scenario 2 | 0.415 | 0.292 | 0.123 | (-0.046, 0.293) | > 0.0615 | 0.773 | > 0 | 0.907 | |
| Scenario 3 | 0.435 | 0.292 | 0.143 | (-0.027, 0.313) | > 0.0615 | 0.835 | > 0 | 0.939 | |
| Scenario 4 | 0.455 | 0.292 | 0.163 | (-0.008, 0.334) | > 0.0615 | 0.885 | > 0 | 0.962 | |

4 Change to protocol specified analyses

Per protocol Section 12.4.4, ASAS40 response in active nr-axSpA participants at Week 16 was supposed to be evaluated using a non-parametric regression model as a “sensitivity analysis”. This analysis has been removed (SAP Section 2.5.4), considering the non-parametric regression model will target the odds ratio, while the primary estimand targets the marginal difference as the summary measurement. Additionally, no evidence for lack of robustness was identified from the global pivotal study CAIN457H2315.

Per protocol Section 12.5.2, Qualitative changes of ECG were supposed to be summarized. But the qualitative changes (interpretation) of ECG were not collected in CRF and hence will not be analyzed (SAP Section 2.7.4.1).

5 Appendix

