5.5.1.1 Logistic regression

Certain binary outcome variables, e.g. response outcomes, will be evaluated using a logistic regression model with treatment as factor and weight as a covariate. The marginal standardization method will be used to calculate the mean response rate in each treatment group as well as their difference. This method uses the same fitted logistic model, but involves using the model to predict, for each patient in the study, the mean outcome assuming assignment to each particular treatment group in turn, assuming each patient's observed values for the other baseline covariates (i.e., weight). Averaging these predictions for each treatment group provides

the estimate of the mean response rate for each treatment group. Then the difference will be derived based on the estimated mean response rates comparing s.c. regimen vs. placebo.

SAS code example as the following,

```
options validvarname=v7;  
%Margins(data      = mydata,  
         class     = treatments strata,  
         response  = AVAL,  
         roptions  = event = '1',  
         model    = treatment baseline_weight strata,  
         dist     = binomial,  
         margins  = treatment,  
         options   = cl diff)
```

If convergence is not obtained the following sequential steps will be used:

1. Remove *strata*. If still no convergence, perform exact test

When exact test is applied, the risk difference and confidence intervals will be estimated via PROC FREQ and EXACT statement.

Input dataset should only contain data from the two treatment groups to be compared.

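### The ASAS responder models, including the primary one, adjust for no baseline symptom score; adding baseline BASDAI could recover a small amount of precision

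*SAP*

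**What the plan says.** SAP 2.5.2 states for the primary model: "The primary analysis will be conducted via logistic regression with treatment and stratification factor" (the three CRP/MRI groups), with weight as the only covariate. Protocol 12.4.2 has the same terms, and the example code in SAP 5.5.1.1 lists "treatment baseline_weight strata" as the model.

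In SAP 2.6.2, each of the other ASAS response rates (ASAS40 overall, ASAS 5/6, ASAS20, partial remission) has those three terms and nothing else. The usual phrase is that the proportion "will be evaluated using a logistic regression model with treatment group and stratification factor", followed by weight. BASDAI50 in the same section differs: it has treatment and stratum "as factors and baseline weight and baseline BASDAI score as covariates". The models for BASDAI, hsCRP, BASFI, SI joint edema, SF-36 PCS and ASQoL each include the baseline value of their own endpoint.

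SAP 2.3.2 lists among the summarised baseline variables "total back pain (VAS), nocturnal back pain (VAS), total BASDAI score, spinal pain (BASDAI question #2), total BASFI score", so the scores are available.

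On the estimator, SAP 5.5.1.1 says: "The marginal standardization method will be used to calculate the mean response rate in each treatment group as well as their difference". If the model does not converge, strata are removed first, and then an exact test is used.

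Protocol 12.4.4 allows optional further logistic models that explore other baseline or disease characteristics. It names no covariates. Neither document gives a reason for leaving a baseline score out of the ASAS models.

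**The concern.** ASAS responses are built from symptom and function scores. ASAS40, ASAS20 and ASAS 5/6 are defined by change from baseline, and partial remission by a low final value. Baseline level may therefore predict who responds. The CRP/MRI stratum carries objective inflammation at screening; it does not carry symptom severity.

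With about 60 TNF-naive participants per arm, the arms can differ by chance in baseline symptoms. A prognostic covariate named in advance removes that part of the random error. The study follows an estimation strategy, and one of its planning criteria is an observed difference above 6.15 points, so the spread of the point estimate matters directly. Because the reported effect is a marginal difference obtained by standardization, adding a baseline covariate would not change what is estimated or disturb the comparison with the global study.

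**Working it through.** **Inputs.** SAP 3.1 says the global study "showed a placebo response rate of about 29.2% and a secukinumab 150 mg response rate of 41.5" per cent for ASAS40 in TNF-naive participants. It plans 120 TNF-naive participants out of 134, 1:1, so 60 per arm, with criteria of an observed difference above 0.0615 and above 0. The prognostic strength of baseline BASDAI is not in the documents. It is assumed here to be an odds ratio of 1.0 to 2.5 per SD, or equivalently a share of outcome variance explained (R²) of 0 to 0.20.

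**1. Reproduce the plan's figures.** Take two independent binomials with n = 60, p1 = 0.415 and p2 = 0.292.
- P(difference > 0.0615) = 0.7730 (stated 0.773).
- P(difference > 0) = 0.9072 (stated 0.907).
- SE = sqrt(0.415 × 0.585/60 + 0.292 × 0.708/60) = 0.0866.
- 95% CI = 0.123 ± 1.96 × 0.0866 = (-0.047, 0.293); stated (-0.046, 0.293).

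The stated figures describe an unadjusted comparison and take no credit for any covariate.

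**2. Formula for the gain.** SE after adjustment ≈ 0.0866 × sqrt(1 - R²). P1 is the normal-approximation probability of exceeding 0.0615.

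| R² | SE | 95% half-width | P1 |
|---|---|---|---|
| 0 | 0.0866 | 0.170 | 0.761 |
| 0.05 | 0.0844 | 0.165 | 0.767 |
| 0.10 | 0.0821 | 0.161 | 0.773 |
| 0.20 | 0.0774 | 0.152 | 0.787 |

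P1 rises by 1.2 points at R² = 0.10 and by about 2.5 points at R² = 0.20.

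**3. Simulation.** There were 10,000 trials per setting, with 60 per arm, marginal rates 0.415 and 0.292, and one standardized baseline covariate. The unadjusted difference is compared with the covariate-adjusted standardized difference. Stratum and weight are left out, so this shows the most the covariate could add.

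| Odds ratio per SD | Variance ratio, adjusted/unadjusted | Shift of unadjusted estimate at 0.3 SD imbalance (points) | Variance share due to imbalance |
|---|---|---|---|
| 1.0 | 1.008 | about 0 | 0 |
| 1.25 | 1.002 | 1.7 | 1.5% |
| 1.5 | 0.977 | 2.7 | 3.6% |
| 2.0 | 0.916 | 4.1 | 8.0% |
| 2.5 | 0.860 | 5.5 | 14.3% |

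At odds ratios of 1.25 to 2.5 the adjusted estimate shifts by only about 0.2 points or less at the same imbalance. Both estimators are unbiased over all trials. The simulated probability of exceeding 0.0615 changed by less than 1 point in either direction.

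**4. Imbalance and precision are one quantity.** The SD of the standardized baseline difference is sqrt(2/60) = 0.183. An imbalance above 0.2 SD in either direction has probability 27%, and above 0.3 SD 10%. The last column rescales the shift to a one-SD imbalance and squares it against the SD of the unadjusted estimate. At odds ratio 2.5: 5.45 × 0.183/0.3 = 3.32 points; (3.32/8.77)² = 14.3%. That matches the simulated variance reduction of 14%. At weak prognostic strength, the cost of estimating one more parameter (about 1%) absorbs the gain.

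**5. Model size.** Expected responders are 60 × 0.415 + 60 × 0.292 = 24.9 + 17.5 = 42.4. The planned model has four parameters besides the intercept (treatment 1, stratum 2, weight 1): 42.4/4 = 10.6 events per parameter. With BASDAI: 42.4/5 = 8.5.

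**The case against.** The strongest reply is that nothing here is an error. Randomization is stratified on CRP/MRI status, the model adjusts for stratum and weight, and the sample size figures hold without any covariate. The size of any gain is assumed. All of this stands.

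Several stronger readings are tempting, and the documents do not support them:

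- **That the contrast with BASDAI50 is an inconsistency.** BASDAI50 and the continuous endpoints each adjust for their own baseline score. An ASAS composite of several domains has no single baseline of its own. The contrast shows only that adjustment is feasible.
- **That chance imbalance is a further harm on top of lost precision.** Step 4 shows that it is the same variance. Setting a 0.3 SD shift beside the 6.15-point criterion can alarm, but that random error is already inside the planned confidence interval, whose half-width is about 17 points.
- **That low baseline scores rule out response.** ASAS40 needs three of four domains, so a BASFI below 2 does not prevent it. The 2-unit rule binds only below a domain baseline of 5, where 40% equals 2 units, and entry already requires at least 4 on BASDAI, spinal pain and total back pain. ASAS 5/6 has no absolute-unit rule. Total BASDAI shares only its two stiffness questions with the main ASAS domains, so it is an imperfect proxy.
- **That prior TNF inhibitor use should also be added to the overall-population models.** It concerns about 134 - 120 = 14 participants, too few to justify another parameter.

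The optional models in Protocol 12.4.4 do not fully answer the point, because a covariate chosen after unblinding is less convincing than one named beforehand. However, the SAP history places supportive analyses in section 2.5.4, which cannot be read in the public text. An adjusted supportive model there cannot be ruled out.

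**Conclusion.** The point holds as a modest efficiency matter, to be considered. All five ASAS responder analyses omit a baseline symptom score that the trial collects. A reader might infer that the primary estimate is biased or the stated probabilities of success are wrong; neither follows. Randomization keeps the planned estimate unbiased, and the figures reproduce.

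Under an assumed odds ratio of 1.0 to 2.5 per SD, adding baseline BASDAI changes the variance of the marginal difference by about +1% to -14%. The probability of exceeding 6.15 points rises by at most 1 to 3 points, and may not rise at all. These are upper bounds, because stratum and weight were left out of the simulation. If baseline BASDAI does not predict ASAS response, there is no gain.

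**What to change.** If the Week 16 treatment codes are still closed:

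- In SAP 2.5.2, 2.6.2 and 5.5.1.1, add baseline BASDAI as a single covariate to the ASAS40 (primary and overall), ASAS20, ASAS 5/6 and partial remission models, and keep marginal standardization.
- Amend the convergence steps in 5.5.1.1 so that baseline BASDAI is dropped before strata. As written, a failure caused by the new covariate would first cost the stratification factor.
- Keep the stratum-plus-weight model as a supportive analysis.

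If those codes are already open, leave the primary model as planned and report the BASDAI-adjusted model as a labelled supplementary analysis. The documents do not settle which case applies: the changes in SAP Amendment 2 (8 January 2025) are marked as made before the Week 52 lock, and Protocol 6.4 has sponsor staff other than field monitors unblinded at the primary endpoint analysis.

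The cost is a few lines of SAP text and code, no new data, and one more parameter (about 8.5 instead of 10.6 expected responders per parameter). That supports one added score, but hardly all four ASAS components.
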